1
2
3
4
5
6
7
8
9
10
11
12
13
14
15
16
17
18
19
20
21
22
23
24
25
26
27
28
29
30
31
32
33
34
35
36
37
38
39
40
41
42
43
44
45
46
47
48
49
50
51
Brooke Army Medical Center
Institutional Review Board

**HUMAN SUBJECTS RESEARCH
PROTOCOL APPLICATION – Part B**

1. PROTOCOL TITLE: Heated Ultrasound Gel Satisfaction (HUGS): A Randomized Control Trial

2. ABSTRACT: Ultrasound has become one of the fastest growing diagnostic tools for Emergency Physicians, and given the increasing focus on patient satisfaction in the Emergency Department, there may be opportunities to enhance both patient satisfaction and diagnostic accuracy. The purpose of this single-blind, randomized control trial will be to investigate whether simply having warm gel, as compared to room-temperature gel, during a bedside ultrasound significantly improves patient satisfaction scores. If satisfaction scores are significantly higher, then medical directors may find it beneficial to invest in ultrasound gel warmers. We will also investigate two secondary hypotheses: 1) patient perceptions of their medical providers and 2) the overall quality of ultrasound images obtained.

3. OBJECTIVES/SPECIFIC AIMS/RESEARCH QUESTIONS.
Hypothesis: The utilization of warmed ultrasound gel significantly increases patient satisfaction with regards to their care during a visit to the Emergency Department.
Null: The utilization of warmed ultrasound gel does not change patient satisfaction with regards to their care during a visit to the Emergency Department.

Hypothesis 2: Utilization of warmed ultrasound gel significantly improves the quality of images obtained during bedside ultrasound.
Null: The utilization of warmed ultrasound gel does not change the quality of images obtained during bedside ultrasound.

Hypothesis 3: The utilization of warmed ultrasound gel significantly increases patient perceptions of their physician's professionalism.
Null: The utilization of warmed ultrasound gel does not change patient perceptions of physician professionalism.

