62 patient in the long run. For example, one abdominal CT delivers 8mSv, which is roughly equivalent to the
63 radiation from 400 chest x-rays.⁴ To counter this increase in CT scans, ultrasounds have become one of the
64 fastest growing and safer diagnostic tools for ED physicians over the past decade. Non-cardiac ultrasound
65 use increased by 121% from 2002-2012, with 21 patients per 1000 being scanned.³ With real-time
66 diagnostic capabilities at the bedside and no harmful radiation, ultrasounds provide clinicians with decision
67 tools to better care for their patients. Class I medical devices, such as the Thermasonic® Gel Warmer, heat
68 ultrasound gel to- and just-above normal body temperatures are frequently seen in Cardiology and OB-GYN
69 clinics, where echocardiograms and pelvic ultrasounds are performed routinely. Given the increase in use of
70 ultrasound and the increased focus on patient satisfaction, our aim is to identify whether warmed gel can
71 truly improve overall patient satisfaction when performing point-of-care ultrasounds in the ED.

72 **6. RESEARCH DESIGN**

73 This is a single-blinded, randomized study will recruit a sample of 124 subjects from military and civilian
74 populations who are treated in the Emergency Department (ED) at SAMMC and require standard of care
75 bedside ultrasound for diagnosis.

76 **7. RESEARCH PLAN**

77 **7.1 Selection of Subjects**

82 **7.1.1. Subject Population.**

84 **7.1.2 Inclusion Criteria:**

- 85 • Adults 18-89 who are seen in the SAMMC Emergency Department that require standard of care
86 bedside ultrasound

88 **7.1.3 Exclusion criteria:**

- 89 • Minors under age 18
- 90 • Pregnant females
- 91 • Adults over age 90
- 92 • Vulnerable adults to include those with altered mental status, incarcerated, military basic trainees, or
93 those with a primary language other than English
- 94 • Patients with open or broken skin

96

7.1.2. Source of Research Material.

Source of Research Material	Clinical Purposes(Y/N)	Research Purposes (Y/N)
Patient Survey	N	Y
Provider Survey	N	Y
Bedside Ultrasound	Y (standard of care)	Y

97

98

99 **7.1.3. Description of the Recruitment and Prescreening Process.** Patients being treated in the ED who
100 require a standard of care bedside ultrasound for diagnosis will be approached by the AI (ultrasonographer).
101 The AI will advise patient that they are there to perform the ultrasound as ordered by his or her doctor and

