136 **7.3. Study Procedures/Research Interventions.** The principal investigator will brief ED physicians on details

137 of this study by email (Appendix D). ED physicians who identify that a patient will require an ultrasound will
138 page the ultrasound team as part of standard of care. At that time, the AI (ultrasonographer) will ask subject if
139 he/she would like to participate in a research study involving patient satisfaction and diagnostic bedside
140 ultrasound. If the patient agrees, the AI will provide an information sheet (Appendix C) and explain study
141 details/answer any questions. The patient will then be randomized and assigned a HUGS-X number that will be
142 placed in the comments section of the ultrasound image and given a 3-question patient survey (Appendix A)
143 related to patient satisfaction and perceptions about their provider which will be completed at the end of the
144 ultrasound procedure. The patient will be instructed not to provide any PII/PHI when he/she completes the
145 survey after the diagnostic bedside ultrasound and to hand it back to the AI when complete.

146
147 **Ultrasound and Warm or Room Temp Gel Procedures:**
148

149 The AIs will use either the warm or cold gel to complete their standard of care diagnostic ultrasound scans.
150 Subjects will be randomized to receive either warm or cold gel depending on the study packet number. The
151 study packet number will contain specific randomized instructions for the AI that provides the appropriate gel
152 numbered 1-6 to utilize and the 3-question patient survey and 1 question provider survey.

153 Patients and providers will be blinded to the intervention meaning both the AI and the patient will be
154 unaware of different gel temperatures being utilized until the moment it is used on the patient's ultrasound
155 area.

156 The provider (AI) will be blinded to the intervention used in two ways. The first being that six ultrasound gel
157 warmers, labeled #1-6, will be set up at a station, and the warmers will have been randomly set-up as far
158 which are actually turned on or not by the PI. The AI will not know which are turned on because the indicator
159 lights will be covered with black tape. Additionally, the AI will use heat-resistant gloves to hold the
160 ultrasound gel bottle as described in section 7.2.2. At the end of the subject's bedside ultrasound, the

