193 Primary Outcome #1a: Overall, how satisfied are you with the experience of having a bedside ultrasound today?
194• Ranges from “Least” to “Most” on 10cm VAS (continuous data)
195

196 Primary Outcome #1b: Overall, are you satisfied with the care you received today in the Emergency
197 Department?
198• “Yes” or “No” (binary data)
199

200 Secondary Outcome #1: Overall, how professional was the physician who did your bedside ultrasound?
201• Ranges from “Least” (1) to “Most” (5) on 5-point Likert-type scale (ordinal data)
202

203 The subject survey form will not contain any PHI/PII. Completed packets will be taken to the locked bin in C-Pod
204 of the Emergency Department. We will also store the completed provider surveys in the same container to allow
205 for further evaluation of provider answers regarding which type of gel they believe they used and if the blinding
206 method imposed by the PI prevented the provider from knowing which gel they utilized.
207

208 New study packets will be kept in a separate designated bin within the Emergency Department, next to the
209 ultrasound gel warmers, so that associate investigators may access all required materials while working in the
210 department. The PI or available AI will pick up completed packets weekly and will either log the data
211 immediately or store them in the designated locked bin in the ultrasound team room until they can be entered
212 into the HUGS DataTracker spreadsheet.
213

214 Subject bedside ultrasounds, like any clinical ultrasound done in our hospital, are uploaded automatically to the
215 IMPAX system. Each week, the SAMMC ED/Ultrasound Quality Assurance Team reviews all bedside
216 ultrasounds for quality assurance purposes. Their standard metric for evaluation is a 5-point Likert-type scale.
217 This type of data is ordinal (and is the basis for secondary outcome #2). These scores will be logged by the PI or
218 available AI into an Excel Spreadsheet found on a password-protected computer behind a locked door in the
219 ultrasound team room. As all investigators are blinded to which ultrasounds were conducted with warm or cold
220 gel, there is no concern for a bias regarding the rating of quality for each ultrasound or during entering survey
221 data to the HUGS DataTracker. Upon transfer of all data to the spreadsheet, the paper surveys and hand-
222 written scores for each ultrasound will be shredded.
223

224 **7.4 Statistical Consideration**

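### The assurance that all investigators are blinded, so that rating and data entry carry no risk of bias, is not secured by the protocol's own procedures

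*Combined protocol and SAP*

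**What the plan says.** The protocol describes blinding in three ways.

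- **Single-blind.** Section 2 (Abstract): "The purpose of this single-blind, randomized control trial will be to investigate whether simply having warm gel" improves satisfaction. Section 6 (Research Design): "This is a single-blinded, randomized study will recruit a sample of 124 subjects from military and civilian" populations.
- **Patients and providers, up to a point in time.** Section 7.3: "Patients and providers will be blinded to the intervention meaning both the AI and the patient will be" "unaware of different gel temperatures being utilized until the moment it is used on the" patient. The AI is the associate investigator who performs the scan. Taped indicator lights and heat-resistant gloves are meant to hide the temperature, and a one-question provider survey tests whether the AI was aware of it.
- **All investigators.** Section 7.3.2: "As all investigators are blinded to which ultrasounds were conducted with warm or cold" gel, there is said to be no concern about bias in rating image quality or entering survey data.

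On who does what, section 7.3 says six numbered warmers are set up at random as to "which are actually turned on or not by the PI", and that the "study packet number will contain specific randomized instructions for the AI that provides the appropriate gel", numbered 1 to 6. The weekly quality assurance (QA) team rates the images on a 5-point scale, and scores for study scans are written down and given to the PI. Under sections 7.3.2 and 7.5 the PI or an available AI collects the packets and logs scores and surveys. The paper surveys and hand-written scores are then shredded.

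**The concern.** The sentence in section 7.3.2 presents blinding as an established fact and rules out bias on that basis. For it to be true, nobody who rates, receives or logs data may be able to know a subject's arm. The protocol gives the PI part of the allocation key and a data-handling role. It limits the AI's blinding to the period before rating and logging take place, and it is silent on operators rating their own scans.

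The outcome most exposed is the subjective image rating, which is the sole outcome for Hypothesis 2. For the patient-marked VAS the exposure is limited to reading and transcription, but an error there cannot be traced once the paper is shredded. A reader told that every investigator was blinded would credit the trial with a protection its procedures do not provide.

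**Working it through.** **Step 1. Set the assurance against each role.**

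| Role | What the procedures give | Does it support the assurance? |
|---|---|---|
| PI | Sets the warmers (7.3); receives image scores (7.3); may collect packets and log data (7.3.2, 7.5) | No. The settings alone do not reveal an arm, but settings plus the packet's gel number do. No safeguard against that link appears in the available text |
| AI who scans | Blinding promised until the gel is used; tape and gloves; awareness tested by survey (7.3); may log data (7.3.2, 7.5) | Not established. The AI may or may not know the arm afterwards, and the plan treats this as open to test |
| QA raters | Section 7.3 has physicians "page the ultrasound team as part of standard of care" to obtain the scan; section 7.5 has the department's ultrasonography team review it. The HUGS identifier shows study membership, not arm | Partly. Raters who neither scanned the subject nor set the warmers may well be blind. Overlap with operators is suggested, not proven, and self-rating is not barred |

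**Step 2. Reproduce the plan's sample size.** Inputs from section 7.4.1: difference 11 mm, SD 21 mm, two-sided alpha 0.05, power 0.80.

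n per arm = 2 × (1.960 + 0.842)² × 21² / 11² = 57.2. Rounding up gives 58 per arm, 116 in total, against the stated 114. At 57 per arm the normal-approximation power is 0.799, so the plan's figure is reproduced to within 2 subjects.

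**Step 3. How large a shift would matter?** Suppose there is no true effect, but rating or entry shifts the warm arm by d standard deviations on average. The rejection probability of a two-sided t-test with 57 per arm (114 / 2) comes from the noncentral t distribution with 112 degrees of freedom and noncentrality d × √(57/2). Solving for 10% gives d = 0.1233 (0.1181 with 62 per arm, 124 / 2).

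- VAS: 0.1233 × 21 = 2.59 mm on average.
- Image rating: 0.1233 × 0.8 = 0.099 points, or 0.1233 × 1.0 = 0.123 points. The rating SDs are assumed; the protocol gives none.
- If 25% of warm-arm values are affected, each must move 2.59 / 0.25 = 10.4 mm, or 0.39 to 0.49 points.
- If 50% are affected, each must move 2.59 / 0.5 = 5.2 mm, or 0.20 to 0.25 points.

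**Step 4. False-positive rates for assumed shifts.** Here d = share affected × shift / SD. Rating shifts are 0.1 to 0.3 points with SD 0.8 to 1.0; VAS misreading is 2 to 3 mm, all in one direction, with SD 21 mm.

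| Share of warm arm affected | Image rating, t-test | Image rating, ordinal simulation | VAS, t-test |
|---|---|---|---|
| 25% | 5.2–7.9% | 5.0–6.4% | 5.2–5.4% |
| 50% | 5.8–16.8% | 5.5–11.0% | 5.7–6.7% |
| 100% | 8.3–51.0% | 7.1–30.6% | not the relevant case |

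The simulation used 20,000 trials per cell and an assumed rating distribution of 2 / 8 / 25 / 45 / 20% over scores 1 to 5 (SD 0.94). Warm-arm ratings moved up one category with probability share × shift, capped at 5. The range covers both the t-test and the Mann-Whitney test. It runs lower than the first column mainly because the top category cannot rise. With 62 per arm the first column becomes 5.2–8.1%, 5.9–17.9% and 8.6–54.4%.

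**The case against.** The strongest reply is that no bias has been shown.

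- **Rating is separate from logging.** The QA team scores the image and only then passes the score on, so the PI and the AI merely transcribe it. Only an operator rating his or her own scan reaches the rating itself, and no section puts the scanning AI or the PI on the panel for a given scan. This is right, and it is why the conclusion is confined to an unsupported assurance.
- **The PI's knowledge is inferred.** It needs the packet-to-gel link, and the documents do not say who prepares the packets or holds any list. Part of section 7.5 and Appendices B and G are not available, so a safeguard may be described there. This limits what can be said about missing safeguards. It does not rescue the sentence, because the person who sets the warmers is a named data handler.
- **AI blinding is meant to last.** Tape, gloves and the provider survey show that intention. But a plan that tests whether blinding held cannot also assume that it did.
- **The shifts are assumed, and the primary outcome is hardly touched.** Both are true, and both are carried into the conclusion.
- **Re-rating is a weak remedy.** Images and HUGS numbers stay in IMPAX, so the rating could be repeated. Section 7.5, however, has the anonymous data destroyed after analysis, so re-rating by arm is assured only before then.

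**Conclusion.** The concern holds. Section 7.3.2 claims more than the procedures secure, and the three descriptions of blinding do not agree. The wording conflict is certain. That the PI or an AI would actually know a subject's arm when handling data is possible and not excluded in the available text. Bias in the results is not shown.

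The documents give no basis for estimating the size of any bias. As a guide, an average shift of 0.123 SD doubles the nominal 5% error rate. With up to half the warm-arm ratings affected, the illustrative rate for the image rating is 5.2–16.8% by t-test and 5.0–11.0% in the ordinal simulation; rating by a team rather than one person would dilute this further. The primary VAS stays at 5.2–6.7% under the same shares. The shares, shifts, rating SDs and rating distribution are assumptions; the group size, alpha and VAS SD come from section 7.4.1. This should be fixed, chiefly for Hypothesis 2 and for accurate reporting of blinding.

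**What to change.** 1. Whoever sets the warmers does not read the VAS, log scores or rate images. The warmer settings, and whatever record links packets to gel numbers, stay sealed until data entry is complete.
2. A team member without access to the settings logs the data. Before entry, the gel-number instruction and the provider survey are separated from the patient survey and image score, each carrying the HUGS or packet number so that they can be re-linked afterwards. Where identifiable, the operator who scanned the subject does not log that subject.
3. At the existing weekly QA session, operators do not score their own study scans.
4. Replace the sentence in section 7.3.2 with a statement of who is blinded, to what and until when. Bring sections 2, 6 and 7.3 into line with it.

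The cost is protocol wording, separation of packet contents and reassignment of tasks within the existing team and meeting. No added staff should be needed if the team includes someone who neither set the warmers nor scanned the subject; the protocol does not give the team's size. Scheduling of data entry becomes slightly less flexible. These changes protect rating and data entry only. They do not address how an operator who senses the temperature behaves during the scan.

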161 physician completing the ultrasound will hand the patient a satisfaction survey utilizing visual analog scales.
162 As an additional measure to test our blinding measure, the AI will complete the one question survey to test
163 whether he or she was aware of the warm or room-temperature gel temperature.

164 Both surveys will be collected and stored in a locked box in C-Pod of the Emergency Department until
165 results can be entered in to the electronic spreadsheet (HUGS DataTracker Data Collection Spreadsheet,
166 Appendix G)

167
168 **The Ultrasound Image Rating:**
169

170 Ultrasound image rating is conducted weekly by the SAMMC ED/Ultrasound Quality Assurance Team on a
171 weekly basis. These meetings are already a standard practice in our department to review every ultrasound
172 obtained in the department as a way to obtain feedback from all clinicians about the quality of their
173 ultrasound studies. Their standard metric for evaluation is a 5-point Likert-type scale. During this QA review,
174 scores related to images that have a HUGS ID in the comments area will be written down and provided to
175 the PI. Their standard metric for evaluation is a 5-point Likert-type scale.

176 Table I: Summary of Study Activity/Interventions
177

Assessment:	During ED Visit:	Weekly Ultrasound QA Session:
Screening	X	
Randomization	X	
Bedside Ultrasound	X	
Anonymous Patient Survey Appendix A)	X	
Provider Survey (Appendix B)	X	
Review of Ultrasound Images for Overall Quality		X

178
179 **7.3.1 Collection of Human Biological Specimens.** N/A
180

181 **7.3.1.1 Laboratory evaluations and special precautions.** N/A
182

183 **7.3.1.2 Specimen storage.** N/A
184

185 **7.3.2 Data Collection.** Subject specific data (patient age, gender, and their satisfaction scores) will all be
186 written on the anonymous survey (Appendix A). The primary outcome will be a visual analogue scale, i.e.
187 continuous variable. By collecting a variable with greater data density than a conventional Likert scale (e.g.,
188 ordinal data), this will enable us to use more powerful statistical techniques in analyzing our data so minimizing
189 the possibility of a type II (beta) error. We will further evaluate our secondary outcomes with Likert-type scales
190 to minimize millimeter differences between patient scores. Finally, we will use binary data to evaluate whether
191 patients were overall satisfied with their visit.
192

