225 **7.4.1 Sample Size Estimation.** This study will be developed to assess our primary outcome with a two-tailed
226 alpha of 0.05 and a beta of 0.2 (power of 0.8), with equal numbers in the warm and cold gel groups. Based on
227 previous studies on visual analog scales and patient satisfaction in the Emergency Department, we will be using
228 an effect size of 0.11 (indicating 11mm on the VAS) with a standard deviation of 0.21 (indicating 21mm on the
229 VAS).⁵

Estimate Required Sample Size	114
Estimate Subject Drop Out / Withdrawal	10
Total Enrollment Requirement	124

Enrollment at Each Site	
BAMC	124

233 **7.4.2 Primary (i.e., primary outcome variables) and secondary endpoints.** As discussed in 7.4.1, this study
234 has been powered to detect an effect size of 11mm on the VAS for a statistically significant difference when
235 investigating our primary outcome (1a).

236 #1a: Overall, how satisfied are you with the experience of having a bedside ultrasound today?

237 Ranges from “Least” to “Most” on 10cm on VAS

238 #1b: Overall, are you satisfied with the care you received today in the Emergency Department?

239• “Yes” or “no”

240 #2: Overall quality of images

241• Ranges from lowest quality (1) to highest quality (5) on a Likert-type scale

242 #3: Overall, how professional was the physician who did your bedside ultrasound?

243• Ranges from “Least” (1) to “Most” (5) on Likert-type scale

244 **7.4.3 Data analysis.** The patient satisfaction scores will be compared (warm vs. cold groups) using
245 independent sample t-tests. If the data are ordinal or not normally distributed with equal variances, the
246 equivalent non-parametric test will be used. Independent sample t-tests will also be used to compare the quality
247 ratings of the ultrasound images.

248 **7.5 Confidentiality.** The PI or available AI will pick up completed packets weekly and will either log the data
249 immediately or store them in the designated locked bin in the ultrasound team room until they can be entered
250 into the HUGS DataTracker spreadsheet. It will not be possible to associate survey forms with patient charts.
251 Data from the anonymous surveys will be entered into an Excel Spreadsheet (HUGS DataTracker, Appendix G)
252 which will be stored on a password protected computer behind a locked door. The completed paper surveys will
253 be immediately shredded once entered electronically. Once the data has been analyzed, the anonymous data
254 will be destroyed.

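### Every comparison named in section 7.4.3 is unadjusted although age and gender are on each survey: a small missed gain in precision, not an error

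*Combined protocol and SAP*

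**What the plan says.** **Analysis.** Section 7.4.3 names independent-sample t-tests for the satisfaction scores, with the non-parametric equivalent if the data are ordinal, non-normal or unequal in variance. It then says "Independent sample t-tests will also be used to compare the quality" ratings of the images. It names no covariate, stratification factor or adjusted model, and no test for the yes/no outcome #1b.

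**Covariates.** Section 7.3.2 states that "Subject specific data (patient age, gender, and their satisfaction scores) will all be" entered on the survey form. Age and gender have no stated analytic use.

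**Image quality.** Scores come from the weekly quality review (section 7.3, image rating). The text says that scores for HUGS-labelled images are passed to the principal investigator. It does not list exam type or operator among the study data. Section 7.3.2 describes the five-point score as ordinal.

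**Sample size.** Section 7.4.1 specifies a two-tailed "alpha of 0.05 and a beta of 0.2 (power of 0.8), with equal numbers in the warm and cold gel groups", and "an effect size of 0.11 (indicating 11mm on the VAS) with a standard deviation of 0.21 (indicating 21mm on the" VAS. This gives 114 patients, plus 10 for dropout, making 124.

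**The concern.** Age and gender cannot be affected by the gel, so adjusting for them is legitimate even though the form is completed after the scan. If they predict satisfaction, leaving them out leaves explainable variance in the error term of the primary comparison. Section 7.3.2 justifies the VAS by the wish for more powerful methods and fewer type II errors; using baseline data already in hand serves the same aim.

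For image quality, any standard-of-care bedside scan is eligible, so the scans may be of mixed types. The ordered scan and the attending ultrasonographer appear to be settled before randomisation (sections 7.1.3 and 7.3), so both could properly enter a model if they were recorded.

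Timing matters. Paper surveys and handwritten quality scores are shredded after entry (7.3.2), surveys cannot be matched to charts (7.5), and computer data with subject numbers are deleted on entry to the spreadsheet (14.0). A covariate not captured at the time may be hard to recover, and an adjustment chosen after seeing results would not be pre-specified.

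**Working it through.** **Inputs from section 7.4.1:** difference 11 mm, SD 21 mm, two-sided alpha 0.05, power 0.80, equal arms, 114 evaluable patients (57 per arm). **Assumed:** R², the share of VAS variance explained by age and gender. The documents do not give it, so 0 to 10% is shown.

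**1. The plan's own figure.** Normal approximation: n per arm = 2 × (1.960 + 0.842)² × 21² / 11² = 57.2. That is 114.4 in total, or 116 if each arm is rounded up to 58. The stated 114 is reproduced. At 57 per arm, power is 79.9% by the normal approximation and 79.2% by the t-test. The t-test figure is the reference below.

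**2. Adjusted power for #1a.** With k = 2 covariates and N = 114:
- standard error = 21 × √[(1 − R²) × (2/57) × (1 + k/(N − k − 3))]
- the last factor, 1 + 2/109 = 1.018, is the average cost of chance covariate imbalance
- degrees of freedom = 114 − 2 − 2 = 110
- power comes from the noncentral t distribution with noncentrality 11 / standard error

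| Analysis | Standard error (mm) | Noncentrality | Power |
|---|---|---|---|
| Unadjusted t-test | 3.93 | 2.80 | 79.2% |
| Adjusted, R² = 0 | 3.97 | 2.77 | 78.4% |
| Adjusted, R² = 2% | 3.93 | 2.80 | 79.2% |
| Adjusted, R² = 5% | 3.87 | 2.84 | 80.5% |
| Adjusted, R² = 10% | 3.77 | 2.92 | 82.5% |

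The worst case is a loss of about 0.7 points. Break-even is where 1 − R² = 1/1.018, that is R² just under 2%. The gain is 1.3 points at 5% and 3.3 points at 10%.

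**3. Chance imbalance, in proportion.** Suppose half the patients are of each gender and gender explains 5% of the variance. The difference between genders is then 2 × √0.05 × 21 = 9.4 mm. A 10-point imbalance between arms shifts the treatment difference by 0.10 × 9.4 = 0.9 mm, against a standard error of 3.9 mm.

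**4. Image quality: why few parameters.** On a linear scale, with 10 extra fixed parameters (for example, many exam-type and operator indicators), the standard error changes by √[(1 − R²) × (1 + 10/101)]. This is 0.995 at R² = 10% and 0.94 at R² = 20%, so almost all of the benefit is used up at 10% and a 6% reduction remains at 20%. These factors only illustrate the parameter cost; they do not describe an ordinal model.

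**The case against.** **The unadjusted test is not wrong.** It is valid under randomisation, its type I error already allows for chance imbalance, and it is the test on which section 7.4.1 rests. This stands, and it is why the point is a suggestion.

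**The gain may be nil.** Age and gender must explain more than about 2% of VAS variance to help at all. If none of the 10 allowed dropouts occurs, unadjusted power with 124 patients is 82.5%, the same as the adjusted figure at R² = 10% with 114. This also stands.

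**Stronger readings about image quality do not hold.** A reader might infer that exam type and operator are known for every scan but left out of the tracker. The supplied text lists neither as recorded, and Appendices A, B and G are not shown, so their absence from the tracker cannot be asserted. A reader might also take the quality review, where scans are "obtained in the department as a way to obtain feedback from all clinicians about the quality of their" studies, to mean that the protocol expects quality to differ by operator. Routine quality assurance does not show that, and no between-operator variance is given. Nor can √(1 − R²) be used to size the gain: it is a linear-model factor without covariate cost, whereas adjusting an ordinal model also changes the target to a conditional odds ratio.

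**Collecting more is not quite free.** The study rests on anonymous surveys and waived documentation of consent. An operator code beside a patient's rating of that physician's professionalism changes what is collected and may need IRB consideration. This stands and limits the fix.

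**The fallback clause might already cover the image score.** Section 7.4.3 does move ordinal data to a non-parametric test, but its next sentence assigns the image ratings to t-tests, so the text needs settling either way.

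**Conclusion.** The point holds in a limited form. Every comparison that section 7.4.3 names is unadjusted while age and gender are collected, so a small gain in precision is left unclaimed. It is not an error and does not threaten the validity of the primary result. It does not extend to #1b, for which no test is named.

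For #1a the effect on power at 57 per arm runs from about −0.7 points (R² = 0) to +3.3 points (R² = 10%). This assumes the plan's 11 mm and 21 mm, a t-based analysis, and an R² that the documents do not supply. For image quality no size can be stated: the documents give neither the variance explained by exam type or operator nor the number of categories. What does stand there is the mismatch between a score described as ordinal in 7.3.2 and the t-test assigned to it in 7.4.3.

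**What to change.** 1. **Section 7.4.3, outcome #1a.** Pre-specify a linear model with arm, age and gender and robust standard errors as the analysis, with the unadjusted comparison as support. State what is done if age or gender is left blank.
2. **Section 7.4.3, image quality.** Replace the t-test with an ordinal analysis.
3. **Section 7.3 and Appendix G.** State whether exam type and operator are recorded. If they are not, note a coarse exam-type category with the quality score against the HUGS number before paper records are shredded. If the IRB has no objection, add a non-identifying operator code.
4. **Adjustment for image quality.** Adjust for exam type using few parameters, with the categories fixed in advance.

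**Cost:** a few degrees of freedom (about 0.7 points of power for #1a if age and gender predict nothing), one or two tracker columns, no added patient contact, and possibly a minor IRB amendment.
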